General anesthetic and sedative agents induce highly structured oscillations in the EEG.^{iv} There is growing evidence that these oscillations relate directly to the systems-level mechanisms by which anesthetics produce altered states of consciousness. During normal brain function, oscillations regulate the timing and coordination of brain activity within and between functional systems and circuits. Anesthesia induced oscillations are thought to disrupt this coordinated activity, producing different states of altered arousal depending upon the receptors and circuits upon which the drugs act.^v General anesthesia with sevoflurane is characterized in the EEG by frontally coherent alpha (8–12 Hz), delta (1–4 Hz), and high amplitude slow (0.1–1Hz) oscillations.^{vi} This pattern, observed when adult patients are sufficiently anaesthetized to conduct surgery, is similar to that observed under propofol-induced general anesthesia and suggests a common systems-level mechanism of action.^{vii} Given that the brain rapidly develops and undergoes significant changes from

childbirth into adulthood, anesthesia induced EEG oscillations in children might differ from those of adults, and could vary significantly with age. Characterizing the structure of the EEG in relation to age would help establish the foundations for age-appropriate monitoring of brain states during general anesthesia and sedation in children. We aimed to examine the effects of age on the EEG during general anesthesia, with sevoflurane as the sole hypnotic agent. The EEG is typically described in terms of rhythmic activity and transients. The rhythmic activity is divided into bands by frequency (figure 1 and figure 3).

Objective

Aim:

This study is designed to evaluate the correlation of raw EEG patterns and age under 1.0 MAC sevoflurane.

Study design and purpose

This study is being conducted to evaluate and assess the electroencephalography wave patterns in different age patients undergoing surgery under general anesthesia. The aim of our study is to compare the raw EEG waves in different age patients and analyze any changes in these patterns among various age groups and which of these groups will have the EEG signal of high-frequency waves or low frequency waves. Previous studies have shown that light sedation is often accompanied by decreasing posterior alpha waves and increasing the intensity of frontal/central beta waves.

Sample size: 120

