Based on 6 different age groups from infants to elderly (0-80 years old), we are recruiting 120 patients with an American Society of Anesthesiology score (ASA) I or II, scheduled for elective surgery under general anesthesia lasting less than 2 hours. Each group will have 20 cases.

Methods:

A sample of 120 healthy patients from the Second Affiliated Hospital of Wenzhou Medical University with American Society of Anesthesiologists (ASA) physical status I or II will be randomly selected and included in this study. After obtaining ethical approval and written informed consent, we will enroll 120 patients (ASA I and II), aged 0-80 years of either gender undergoing minor elective surgery. The selected patients will be divided into 6 different groups according to their age (figure 2). The surgeries will last less than two hours each and will be performed under general anesthesia which is an indispensable part of surgery. Depth of anesthesia and electrical brain activity will be monitored using Bispectral index monitoring system. However, these are based on the underlying changes in the features of an EEG signal as the signals vary with the level of anesthesia. We will compare the different EEG waves (alpha, delta, theta and gamma) for all age patients while maintaining 1.0 MAC sevoflurane. Data related to non-invasive blood pressure, heart rate, respiration rate, oxygen saturation, EEG waves frequencies, end tidal volume of sevoflurane and BIS values will be recorded. These data will be analyzed every 1 min for the first 10mins during maintenance of anesthesia with 1.0 MAC sevoflurane. Data collection will be first recorded after tracheal intubation. The raw EEG wave will be recorded by means of a Universal Serial Bus (USB) which will later be analyzed and processed offline.

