120 patients undergoing minor elective surgeries will be allocated in 6 age groups: 1month-1 year old (infant period), 1-3 years old (toddler period), 3-6 years old (preschool age period), 7-18 years old (school age period), 18-65 years old (adults) and 65-80 years old (elderly). After arrival in the operating room, an intravenous line will be inserted into a large forearm vein, and standard monitors will be applied. Each patient will be continuously monitored by a 3-lead electrocardiogram, noninvasive arterial pressure, pulse oximetry, and end-tidal carbon dioxide concentration. In addition to the standard conventional monitors, BIS electrodes will be placed before induction on each patient. The electroencephalogram will be recorded continuously over a period of 10 minutes using the Aspect A-2000 BIS®monitor (version XP). All the 120 patients enrolled in this study will be studied for 10 minutes after induction and tracheal intubation without any surgical stimulus. After the skin of the forehead had been prepared and cleaned with

alcohol, the BIS® (BIS-XP sensor) and BIS electrodes will be positioned as recommended by the manufacturers. Anesthesia will be induced by sevoflurane inhalation only with a tight-fitting facemask and a 4-l airflow of 100% oxygen. As spontaneous breathing diminishes, patients will be manually assisted and with cessation of spontaneous breathing, will be mechanically ventilated via the facemask to an end-tidal carbon dioxide of 35 mmHg. The induction of anesthesia will be the same in all age groups and will consist of sufentanil 0.2-0.3mcg/kg or fentanyl 1-2 mcg/kg before intubation and 0.2 mg/kg cisatracurium to facilitate intubation. Sevoflurane inhalation will be adjusted in all age groups to maintain 1.0 MAC concentration. After tracheal intubation, patients will be ventilated with a tidal volume of 6-8 ml/kg and the respiratory rate will be adapted to obtain an end-tidal carbon dioxide concentration of 30–35 mmHg. After intubation, sevoflurane will be titrated to generate an end-tidal concentration (ETsevo) of 2.0, 3.0, and 4.0% in a stepwise increase or decrease pattern in each age group to maintain 1.0 MAC concentration.

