All patients will be ventilated using an Ohmeda-Datex anesthetic machine with soda lime (CO₂ absorber). Hypotension, defined as a decrease in blood pressure by 25% from baseline, will be treated with intravenous fluid or phenyl ephedrine (20 microgram bolus). Raw EEG data, BIS values and end target expiratory concentration of sevoflurane will be recorded every one minute for a period of 10 mins after induction and intubation. Raw EEG data (figure4-patient of 80 years old), will be analyzed and processed using the pdf screenshot from the BIS vista monitor. The pdf screenshots of the raw EEG will be recorded by means of a Universal Serial Bus (USB). The pdf screenshots will be taken twice during the 10 minutes of recording to minimize any loss of data.

Inclusion Criteria:

Patients age between 0 to 80 years old, ASA I or II scheduled for minor surgeries under general anesthesia lasting less than 2 hours each.

Exclusion Criteria:

Potential subjects with any neurologic or psychiatric disease, relative or absolute contraindication to sevoflurane including pregnancy by patient self-report, and any recent

prescription or illicit medication use will be excluded. Patients with a history of any disabling central nervous or cerebrovascular disease and patients who had received central nervous system-active drugs will be excluded from the study. We will exclude patients with poor quality data, most likely because of poor electrode contact.

Potential benefits

The advantages of this study are to help the anesthesiologist have a better understanding of the brain waves under general anesthesia. EEG monitoring provides assessment of brain perfusion during state of general anesthesia. Brain death during anesthesia can be assessed and prevented with the use of raw EEG patterns.

EEG waves monitoring is a key aspect in preventing brain damage and ensuring the level of anesthesia is within the required range.

Maintaining the required range of deep anesthesia (BIS value of 40 to 60) helps avoid the incidence of awareness with recall in adults during general anesthesia and sedation.

Potential risks

There are no risks and complications associated with this study. However, mild redness may appear on the forehead in some patients from the BIS electrodes.

Statistics:

Statistical analyses will be performed with a statistical package (SPSS version 21.0; SPSS, Chicago, IL) and Microsoft excel. All data will be presented as mean \pm sd.

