**STATISTICAL PLAN:**

Statistical analyses will be performed with a statistical package (SPSS version 21.0; SPSS, Chicago, IL) and Microsoft excel. All data will be presented as mean  $\pm$  sd. Demographic data will be compared by using standard t-tests; comparison of incidence data between groups performed by using Fisher's exact tests. A P value  $< 0.05$  will be considered significant.

Data related to non-invasive blood pressure, heart rate, respiration rate, oxygen saturation, EEG waves frequencies, end tidal volume of sevoflurane and BIS values will be recorded. These data will be analyzed every 1min for the first 10mins during maintenance of anesthesia with 1.0 MAC sevoflurane. Data collection will be first recorded after tracheal intubation. The raw EEG wave will be recorded by means of a Universal Serial Bus (USB) which will later be analyzed and processed offline.

EEG waves , BIS values and Et sevoflurane will be collected every 1minute for a period of 10 minutes at T1,T2,T3,T4,T5,T6,T7,T8,T9,T10.

Non-invasive blood pressure, heart rate, respiration rate and oxygen saturation values will be recorded every 3 minutes for the same period (10minutes).

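### The protocol sets 1.0 MAC for every age group but also directs end-tidal sevoflurane of 2.0, 3.0 and 4.0% in each group; with no target by age in the supplied text, equal MAC across ages is not ensured

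*Protocol*

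**What the plan says.** The condition under which ages are to be compared is stated several times:

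- Protocol, Objective: "This study is designed to evaluate the correlation of raw EEG patterns and age under 1.0 MAC sevoflurane".
- Protocol, Methods: "We will compare the different EEG waves (alpha, delta, theta and gamma) for all age patients while maintaining 1.0 MAC sevoflurane".
- Protocol, Methods (anesthetic procedure): "Sevoflurane inhalation will be adjusted in all age groups to maintain 1.0 MAC concentration".

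The same procedure text then sets the end-tidal sevoflurane concentration after intubation: "ETsevo) of 2.0, 3.0, and 4.0% in a stepwise increase or decrease pattern in each age group to maintain 1.0 MAC concentration".

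On recording, Methods has data collection begin once the trachea is intubated. It adds that "end target expiratory concentration of sevoflurane will be recorded every one minute for a period of 10 mins after induction and intubation". The raw EEG "will be analyzed and processed using the pdf screenshot from the BIS vista monitor", and "The pdf screenshots will be taken twice during the 10 minutes of recording to minimize any loss of data". The SAP, under Statistical plan, describes the window as follows: "These data will be analyzed every 1min for the first 10mins during maintenance of anesthesia with 1.0 MAC sevoflurane".

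Figure 2 lists the six age bands and nothing about dose. The supplied text of both documents gives no end-tidal percentage that counts as 1.0 MAC at any age, no adjustment formula and no tolerance. End-tidal sevoflurane is collected at T1 to T10, but the supplied SAP text does not say what it is used for.

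**The concern.** Anesthetic depth is the factor that this design has to hold equal. Methods states that EEG features change with the level of anesthesia. If the MAC multiple differs between age groups, a difference in EEG bands can come from age, from depth or from both, and the data cannot separate them.

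The titration sentence puts this at risk in one of two ways, depending on how staff read it.

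- **Literal reading.** Every age group passes through 2, 3 and 4%. Patients are then away from 1.0 MAC for part of the recording. If 1.0 MAC differs by age, the groups are compared at equal percentage and not at equal MAC, and the MAC difference runs along with age.
- **Purpose reading.** Staff move the concentration up or down until 1.0 MAC is reached. The sentence is then consistent with the aim, but the value to aim at is left open. Two anesthetists could use different values for patients of the same age.

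Timing adds to the risk on either reading. Titration and recording are both placed after intubation, so they can overlap.

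**Working it through.** **Inputs.** From the protocol's Methods: a target of 1.0 MAC in all groups; levels of 2.0, 3.0 and 4.0%; two screenshots per patient in 10 minutes; six groups of 20. The stated total reproduces (6 × 20 = 120) and is not in dispute. The end-tidal percentage equal to 1.0 MAC, called M here, is not in the documents. It is treated as unknown and varied.

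**Step 1: results that hold whatever M is.** The MAC multiple at level L is L / M. For a fixed M it equals 1.0 at no more than one of three distinct levels. The ratio between two levels does not involve M:

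- 4.0 / 3.0 = 1.33
- 3.0 / 2.0 = 1.50
- 4.0 / 2.0 = 2.00

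A patient taken through all three levels therefore covers a twofold range of MAC multiple.

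**Step 2: allowing a tolerance.** Levels a < b can both lie within ±t of the same M only if b / (1 + t) ≤ a / (1 − t), that is, t ≥ (b − a) / (b + a):

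- 3 and 4%: 1/7 = 0.143
- 2 and 3%: 1/5 = 0.200
- 2 and 4%: 2/6 = 0.333

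For any tolerance tighter than ±14.3%, at most one of the three levels is on target.

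**Step 3: dependence on M (assumed values, tolerance ±10% assumed).** Level L is on target when M lies between L / 1.1 and L / 0.9. This gives 1.82–2.22% for the 2% level, 2.73–3.33% for 3% and 3.64–4.44% for 4%. Outside these ranges no level is on target.

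| Assumed M (%) | Multiple at 2% | Multiple at 3% | Multiple at 4% | Levels within ±10% |
|---|---|---|---|---|
| 2.0 | 1.00 | 1.50 | 2.00 | 1 |
| 2.5 | 0.80 | 1.20 | 1.60 | 0 |
| 3.0 | 0.67 | 1.00 | 1.33 | 1 |
| 3.5 | 0.57 | 0.86 | 1.14 | 0 |
| 4.0 | 0.50 | 0.75 | 1.00 | 1 |

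**Step 4: comparison between ages on the literal reading.** Take two age groups at the same level L, with 1.0 MAC values M1 and M2. Their multiples are L / M1 and L / M2, so they differ by the factor M2 / M1 at every step. If the highest and lowest values across ages differed by a factor of 1.25, 1.5 or 2.0 (assumed), the groups would differ in MAC multiple by 1.25, 1.5 or 2.0.

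**Step 5: the purpose reading.** No arithmetic applies. The departure from 1.0 MAC depends on the values that staff choose and on how soon they reach them, and the supplied text specifies neither.

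**The case against.** The best defence is that the literal reading is the weaker one. The titration sentence allows increase or decrease and ends with the purpose of maintaining 1.0 MAC, and the aim, Methods and SAP all set the same condition. Titrating until 1.0 MAC is reached fits every statement; marching each group through three levels does not. This stands, and a flat claim that the protocol contradicts itself would go too far.

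A second argument is that the SAP already places the window within maintenance at 1.0 MAC. It can be read together with the protocol's start after intubation, and minute-by-minute end-tidal readings would show departures. This stands in part. The window states an intention, but no supplied text makes T1 or a screenshot wait for the target, and no stated analysis uses the readings.

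Some stronger inferences are tempting and are not supported:

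- **That a known share of the EEG screenshots, such as half, will be off target.** This would need every patient's two screenshots to fall at different steps, and a tolerance tight enough that both cannot qualify. The protocol does not say when in the 10 minutes they are taken.
- **That the age comparison is biased.** Bias on the literal reading needs 1.0 MAC to differ by age, which the documents do not state. The factors in Step 4 are assumptions.
- **That no age-specific target exists anywhere.** Part of the SAP and some figures were not available, so the absence is established only for the supplied text.

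**Conclusion.** The point holds as a defect in the procedure text that should be fixed. The titration sentence either contradicts the 1.0 MAC condition or leaves that condition without a usable target, and the documents do not settle which. On both readings, the supplied text does not ensure equal MAC across ages during T1 to T10 or at the two screenshots.

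Without any outside value, it can be said that at most one of the three levels is 1.0 MAC for a patient, that the levels span a factor of 2.00, and that this survives any tolerance tighter than ±14.3%. The range table and the between-age factors rest on assumed values. On the purpose reading no size can be given. The documents do not show that unequal MAC will occur, and the size of any bias in the EEG comparison cannot be derived from them. Confidence is high that the wording is unclear and the target absent from the supplied text; it does not extend to the consequence.

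**What to change.** **Protocol, Methods.**

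1. Delete the 2.0, 3.0 and 4.0% steps.
2. Give the end-tidal sevoflurane value that counts as 1.0 MAC by age, with its source and a tolerance (for example ±10%).
3. Start T1, and take both EEG screenshots, only once the end-tidal reading is within tolerance.

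**SAP, Statistical plan.**

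1. Use the end-tidal readings already collected each minute to report, per age group, the MAC multiple reached: the reading divided by the 1.0 MAC value for that age.
2. Restrict the EEG comparison between ages to in-tolerance data, and repeat it with all data as a sensitivity check.
3. Work with the MAC multiple and not with the raw percentage. If 1.0 MAC differs by age, the raw percentage differs by age by design, and adjusting for it would remove part of the age effect.

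**Cost.** One protocol amendment with a short table of targets, and a few lines in the SAP. No new measurement is needed. The downsides are a short delay before T1, which lengthens the period without surgical stimulus, and possibly a few excluded readings. Taking screenshots only when the level is in tolerance should keep that loss small.

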Demographic data will be compared by using standard t-tests; comparison of incidence data between groups performed by using Fisher's exact tests. A P value < 0.05 will be considered significant.

Study duration:

We are estimating that the entire study will require one year, including patient recruitment, data collection, data analysis and report writing.

Co-Investigators:

Name	Department	Role
[name]	Anesthesiology, The second affiliated hospital of Wenzhou Medical University.	Principal Investigator
[name]	Anesthesiology, The second affiliated hospital of Wenzhou Medical University.	Co-Clinical Investigator

Payment:

There is no financial benefit or any reimbursement for participation in this study.

Figure 1:

Band	Frequency (Hz)
Delta	< 4
Theta	≥ 4 and < 8
Alpha	≥ 8 and < 14
Beta	≥ 14

Figure 2:

Groups	Age
1- Infant period	1month-1 year old
2- Toddler period	1-3 years old
3- Preschool age period	3-6 years old
4- School age period	7-18 years old
5- Adults	18-65 years old
6- Elderly	65-80 years old

Figure 3:

[figure not shown]
[figure not shown]

Figure 4:

References:

ⁱ Prashant J. General growth and tissue development throughout childhood. In: Bruno B, Bernard JD, eds. *Pediatric Anesthesia: Principles and Practice*. New York: McGraw-Hill, 2002; 32–3

ⁱⁱ McCann ME, Bacsik J, Davidson A, Auble S, Sullivan L, Laussen P. The correlation of bispectral index with endtidal sevoflurane concentration and haemodynamic parameters in preschoolers. *Paediatr Anaesth* 2002; 12: 519–25

ⁱⁱⁱ Davidson AJ, McCann ME, Devavaram P, et al. The differences in the bispectral index between infants and children during emergence from anesthesia after circumcision surgery. *Anesth Analg* 2001; 93: 326–30

^{iv} Gibbs FA, Gibbs LE, Lennox WG. Effects on the electroencephalogram of certain drugs which influence nervous activity. *Arch Intern Med* 1937; 60: 154–66

^v Lewis LD, Weiner VS, Mukamel EA, et al. Rapid fragmentation of neuronal networks at the onset of propofol-induced unconsciousness. *Proc Natl Acad Sci USA* 2012; 109: E3377–8

^{vi} Brown EN, Solt K, Purdon PL, Akeju O. Monitoring Brain State During General Anesthesia and Sedation. *Miller's Anesthesia*: Philadelphia: Elsevier, 2014 (Chapter 50)

^{vii} Brown EN, Lydic R, Schiff ND. General anesthesia, sleep, and coma. *The New England Journal of Medicine* 2010; 363:2638–50

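### The phenylephrine option for hypotension is a flat 20 microgram bolus from infancy to age 80, although every other named injected drug is dosed per kg

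*Protocol*

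**What the plan says.** The treatment rule is in the Protocol's Methods, in the paragraph on ventilation and recording that covers all patients. The trigger is "Hypotension, defined as a decrease in blood pressure by 25% from baseline". A patient who meets it "will be treated with intravenous fluid or phenyl ephedrine (20 microgram bolus". I read the two-word drug name as phenylephrine. The line gives no per-kg amount, paediatric tier or adult-only limit, and no rule on repeat boluses.

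The population is wide. Inclusion Criteria read "Patients age between 0 to 80 years old, ASA I or II", and Figure 2 sets the youngest group at "1month-1 year old" and the oldest at 65-80 years.

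The other doses in Methods follow body weight. The Protocol states that "The induction of anesthesia will be the same in all age groups" and that it "will consist of sufentanil 0.2-0.3mcg/kg or fentanyl 1-2 mcg/kg before intubation and 0.2 mg/kg cisatracurium to facilitate intubation". After intubation, "patients will be ventilated with a tidal volume of 6-8 ml/kg". The Statistical Plan section of the SAP contains no dosing that changes any of this; part of the SAP was not available to me.

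**The concern.** Phenylephrine is the only named injected drug in the Protocol with an absolute dose. The inconsistency is internal, so no outside dosing source is needed to see it: Methods ties the opioids, the muscle relaxant and the tidal volume to body weight, then gives one fixed vasopressor amount to patients whose weights must differ many-fold.

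This is a patient-safety point about the basis of the dose. With a fixed amount, the per-kg exposure is largest in the lightest patients. It is also a stated rule and not just a gap, because a clinician who follows the line literally gives a small infant the adult bolus. The fluid option has no stated volume either, but that is missing detail and not part of this point.

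**Working it through.** The 20 microgram figure is a prescribed dose with no derivation, so there is no calculation in the plan to reproduce. The check is a conversion to amount per kg.

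**Inputs from the Protocol (Methods, Figure 2):** phenylephrine 20 microgram per bolus; sufentanil 0.2-0.3 mcg/kg; fentanyl 1-2 mcg/kg; cisatracurium 0.2 mg/kg; groups from 1 month to 80 years.

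**Inputs assumed, because the documents give no weights:** infants 4-10 kg; adults and elderly 50-80 kg.

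**Step 1. Amount per kg = 20 / weight.**

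| Patients | Lightest | Heaviest |
|---|---|---|
| Infants | 20/4 = 5.0 mcg/kg | 20/10 = 2.0 mcg/kg |
| Adults and elderly | 20/50 = 0.40 mcg/kg | 20/80 = 0.25 mcg/kg |

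**Step 2. Infant amount as a multiple of the adult amount.** The smallest is 2.0/0.40 = 5. The largest is 5.0/0.25 = 20. With a fixed dose this is simply adult weight over infant weight: 50/10 = 5 and 80/4 = 20. The upper end pairs the lightest infant with the heaviest adult.

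**Step 3. Other assumed weights.** 5 kg against 60 kg gives 12; 4 kg against 70 kg gives 17.5; 3 kg against 90 kg gives 30. Any infant of 10 kg or less against any adult of 50 kg or more gives at least 5, so the conclusion for infants does not hang on a particular choice.

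**Step 4. Older children.** The multiple falls as weight rises. At an assumed 10-20 kg (toddler and preschool groups) it runs from 1.0/0.40 = 2.5 to 2.0/0.25 = 8. A 25 kg child against a 50 kg adult gives only 2.0. At 20-60 kg (school age) it runs from 0.333/0.40 = 0.83 to 1.0/0.25 = 4. The firm result is the one for infants.

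**Step 5. Contrast with the per-kg drugs, 4 kg against 70 kg.**

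| Drug | 4 kg | 70 kg |
|---|---|---|
| Sufentanil | 0.8-1.2 mcg | 14-21 mcg |
| Fentanyl | 4-8 mcg | 70-140 mcg |
| Cisatracurium | 0.8 mg | 14 mg |
| Phenylephrine | 20 mcg | 20 mcg |

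The first three amounts rise 17.5-fold with weight (70/4). The phenylephrine amount does not change.

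All figures are per bolus.

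**The case against.** The strongest reply is that this is rescue care and not a study intervention. Fluid is listed first, patients are ASA I or II, and they are under blood pressure monitoring with anesthesia staff present. An experienced anesthesiologist would probably reduce the bolus for an infant. All of that may be so, and it limits the likely consequence. It does not change the text, which gives a number and no discretion over it. If adjustment is intended, writing it down costs one line.

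A reader might also infer more than the documents support:

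- **That the infant amount is an overdose.** The documents give no paediatric phenylephrine dose and no harm data. The multiples are weight ratios, not evidence of toxicity.
- **That a known number of children is exposed.** Sample size says "Each group will have 20 cases", so the four groups up to age 18 hold 4 x 20 = 80 of the 120 patients. Those are planned enrolments. No hypotension rate is given, and only patients who meet the trigger and receive the drug instead of fluid are affected.
- **That the width of the fentanyl range, 2/1 = 2.0-fold, is the Protocol's tolerance for per-kg differences.** It is latitude for one opioid at induction and says nothing about how a vasopressor may differ by age.
- **That the EEG comparison across ages is biased.** Nothing in the documents shows an effect of the bolus on the EEG results, and none is claimed.

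**Conclusion.** The point holds as a cheap improvement to the Protocol. The text establishes that the phenylephrine bolus is fixed at 20 microgram for all ages, that nothing I could see in either document scales it or limits it to adults, and that every other named injected drug is per kg. On that narrow statement confidence is high.

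The size depends on assumed weights: 5 to 20 times the adult per-kg amount in infants, for infants of 4-10 kg and adults of 50-80 kg. Harm and the number treated are not established. Sample size, power and the planned analyses are unaffected.

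**What to change.** Amend the hypotension line in Methods to read: *intravenous fluid or phenylephrine (patients under 18 years: a weight-based bolus of [X] microgram/kg, maximum 20 microgram; patients 18 years and over: 20 microgram bolus).*

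The responsible paediatric anesthesiologists should set X before enrolment. The documents contain nothing from which to derive it, so no value is proposed here. One check applies: X should be low enough that the maximum does not simply reproduce the flat dose in infants. The maximum takes effect at weights of 20/X and above. As an illustration, X = 5 would give the full 20 microgram from 20/5 = 4 kg upward, which is the present rule across the whole assumed infant range.

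Wording the split by age instead of by group number covers any patient under 1 month, whom the Inclusion Criteria admit but Figure 2 does not place. It also avoids a conflict at age 18, which Figure 2 puts in both the school-age and adult groups.

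The cost is one line of amendment and a bedside calculation from a body weight that the opioid, cisatracurium and tidal volume already require. No patients or data items are added. A smaller paediatric bolus may need repeating, which the Protocol does not forbid. Because of the maximum, no single bolus would exceed what the current line allows.

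### Neither the offline reading of the EEG screenshots nor the exclusion of poor-quality recordings is masked to age, the variable under study; coding the files would be a cheap safeguard.

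*Protocol*

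**What the plan says.** The Protocol's Objective states the aim: "This study is designed to evaluate the correlation of raw EEG patterns and age under 1.0 MAC sevoflurane". Patients are grouped by age (Figure 2), and "Each group will have 20 cases".

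On how the EEG is obtained and read, the Methods say: "The raw EEG wave will be recorded by means of a Universal Serial Bus (USB) which will later be analyzed and processed offline". They then name the material: "Raw EEG data (figure4-patient of 80 years old), will be analyzed and processed using the pdf screenshot from the BIS vista monitor". On the number of images: "The pdf screenshots will be taken twice during the 10 minutes of recording to minimize any loss of data". The SAP's statistical plan repeats that the trace is one "which will later be analyzed and processed offline" and adds no masking step.

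The Exclusion Criteria remove patients whose data are of poor quality and give poor electrode contact as the likely cause. They do not say who decides, when, or by what measure.

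The Background raises the possibility that EEG oscillations under anaesthesia in children differ from those in adults and vary with age. It states no direction.

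The only software named, in the Statistics section and the SAP, is SPSS and Microsoft Excel. Neither document mentions masking, coded files, an independent reader or a second reader.

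**The concern.** Age is the exposure and cannot be randomised, so allocation gives no protection against a biased reading. Masked assessment is one of the few safeguards such a design can have. Because the EEG is read after the case from stored files, that safeguard is available here.

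Knowledge of age could enter in two places:

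- **Turning a trace into band measures.** The rules leave some discretion. Alpha runs from 8 to 12 Hz in the Background but from 8 to below 14 Hz in Figure 1. The Methods plan to compare gamma, which Figure 1 does not define, and leave out beta, which it does.
- **The quality exclusion.** With no objective criterion, a trace that looks unusual for the patient's age could be dropped or kept partly for that reason.

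Either could create, enlarge or hide a difference between age groups, and the analysis could not separate this from a true age effect.

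**Working it through.** **Side by side**

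| Step | What the documents give | What they leave open |
|---|---|---|
| EEG reading | Offline, from pdf screenshots (Protocol, Methods; SAP) | Reader, by eye or by software, scoring rule beyond the band table, masking |
| Quality exclusion | Poor-quality data excluded (Protocol, Exclusion Criteria) | Who decides, criterion, timing, masking |
| Prior expectation | Children might differ from adults (Protocol, Background) | Direction; nothing stated for the elderly |

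**Counts from the plan**

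- Sample size: 6 groups × 20 = 120, which reproduces the Protocol's "Sample size: 120".
- Screenshots: 2 per patient × 120 = 240. This is a maximum. The second image is taken to guard against loss, so it may serve only as a backup.

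**Hypothetical scale**

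The plan gives no SD, effect size or power, and names no test for the EEG measures. The following therefore rests on assumptions: no true age difference, normal data, one reading per patient, a two-sided 5% level (the plan gives P < 0.05 without sidedness), and a reader who shifts one whole group by b SD.

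*Two groups of 20, t-test.* Degrees of freedom are 20 + 20 − 2 = 38. The noncentrality is b / √(2/20) = b / 0.316.

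- b = 0.2: 0.2 / 0.316 = 0.63
- b = 0.5: 0.5 / 0.316 = 1.58

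*Six groups of 20, F test, one group shifted.* Degrees of freedom are 5 and 114. The noncentrality is 120 × b² × (1/6)(5/6) = 16.67 b².

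The probability of a false-positive result, from the noncentral t and F distributions, is:

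| Assumed shift b (SD) | t-test, that pair | F test, six groups |
|---|---|---|
| 0 | 5.0% | 5.0% |
| 0.1 | 6.1% | 5.7% |
| 0.2 | 9.5% | 8.0% |
| 0.3 | 15.2% | 12.3% |
| 0.5 | 33.8% | 29.0% |

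Masking changes none of the plan's figures. N stays at 120, each group at 20 and the significance level at 0.05. Where masking works, the rates move back towards 5%.

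**The case against.** The strongest reply is that silence is not a statement that readers will know the age. Reading by eye is also an inference. The documents say only that the trace is analysed and processed, and Figure 1 gives numeric band limits. Automated extraction with one fixed setting would leave little room for bias. This stands, and it is why the point is conditional on some judgement being involved. Two facts keep that condition plausible: the source is an image, and no signal-processing software is named. The quality exclusion is a separate opening, whichever way the bands are read.

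A reader might go further in several ways that the documents do not support:

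- **That the reader will see the age because the example is tagged as an 80-year-old.** The tag describes an illustrative figure in the Protocol. It does not show that study files carry the age.
- **That the person who reads the EEG also makes the quality exclusions.** Nobody is assigned to either task.
- **That readings would be pulled in an expected direction for infants or the elderly.** No direction is stated for children, and no expectation at all for the elderly. The Protocol asks openly which groups show high-frequency or low-frequency waves. What remains is a possible general lean towards finding a difference.
- **That the false-positive rate will be 10% to 34%.** The shift is assumed, and the plan assigns t-tests to demographic data only.

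It is also fair to say that masking may be incomplete. The trace may suggest the age, and the Protocol lists only two investigators, both in anaesthesiology, who may also be present at the cases. This limits the benefit without removing it. BIS and end-tidal values come from devices and are less exposed.

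**Conclusion.** The point holds in a limited form. The study's central comparison is of EEG patterns by age. The EEG is processed offline from screenshots, recordings can be dropped for poor quality without an objective criterion, and the available text masks neither step to age. The SAP text available to this review was not complete, so the finding is limited to what could be read.

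The documents do not show that bias will occur, how large it would be, or which way it would go. If a shift of 0.2 to 0.5 SD did arise between two groups of 20, a two-sided 5% t-test would be falsely significant in about 10% to 34% of studies instead of 5%. Those figures indicate scale only. No primary outcome is formally named, so the weight given to the EEG reading rests on the stated aim.

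This is a low-cost improvement that should be made. It is not a defect that invalidates the study.

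**What to change.** Add a short procedure to the Protocol's Methods, where the screenshots are described, and to the SAP:

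1. A member of the existing team codes the screenshot files, removes name, age and date, and shuffles them across age groups. Any other stored EEG used for the readings is treated in the same way.
2. The text states who reads the files, and whether by eye or by software. Band measures follow one written rule or one fixed software setting for all ages, with band limits that agree throughout the documents.
3. The poor-quality criterion is written down and applied to the coded files.
4. Band measures and exclusions are completed and locked before the code is broken.
5. Exclusions are reported by age group.

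The cost is a few hours of file coding for at most about 240 screenshots. This is a judgement, since the documents do not show what is printed on the files. No patient procedure or sample size changes, and no extra reader is required. A reader who was not in the operating room would mask better where one is available. If the reader was present, or if the trace itself suggests age, masking is only partial and the report should say so.
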